## APPENDIX B1: PRIMARY MYELOFIBROSIS DEFINITION

### 2008 WHO Diagnostic Criteria for primary myelofibrosis (PMF)

Diagnosis requires meeting all 3 major criteria and 2 minor criteria	
Major criteria	

1. Presence of megakaryocyte proliferation and atypia,* usually accompanied by either reticulin or collagen fibrosis, or, in the absence of significant reticulin fibrosis, the megakaryocyte changes must be accompanied by an increased bone marrow cellularity characterized by granulocytic proliferation and often decreased erythropoiesis (ie, prefibrotic cellular-phase disease)

2. Not meeting WHO criteria for polycythemia vera,† BCR-ABL1-positive chronic myelogenous leukemia,‡ myelodysplastic syndrome,§ or other myeloid disorders

3. Demonstration of JAK2 V617F or other clonal marker (e.g., MPLW515K/L), or, in the absence of the above clonal markers, no evidence that bone marrow fibrosis is secondary to infection, autoimmune disorder or other chronic inflammatory condition, hairy cell leukemia or other lymphoid neoplasm, metastatic malignancy, or toxic (chronic) myelopathies  

Minor criteria	

1. Leukoerythroblastosis¶

2. Increase in serum lactate dehydrogenase level¶

3. Anemia¶

4. Palpable splenomegaly¶

\*Small to large megakaryocytes with an aberrant nuclear/cytoplasmic ratio and hyperchromatic, bulbous, or irregularly folded nuclei and dense clustering.

†Requires the failure of iron replacement therapy to increase hemoglobin level to the polycythemia vera range in the presence of decreased serum ferritin. Exclusion of polycythemia vera is based on hemoglobin and hematocrit levels. Red cell mass measurement is not required.

‡Requires the absence of *BCR-ABL1*.

§Requires the absence of dyserythropoiesis and dysgranulopoiesis.

||It should be noted that patients with conditions associated with reactive myelofibrosis are not immune to primary myelofibrosis, and the diagnosis should be considered in such cases if other criteria are met.

¶Degree of abnormality could be borderline or marked.

Reference: Vardiman J, Thiele T, Arber D, et al. The 2008 revision of the World Health Organization (WHO) classification of myeloid neoplasms and acute leukemia: rationale and important changes. *Blood*.2009; 114:937-951.

## APPENDIX B2: POST-POLYCYTHEMIA VERA MYELOFIBROSIS DEFINITION

### 2008 IWG-MRT Diagnostic Criteria for post-polycythemia veramyelofibrosis (post-PV MF)

#### Required criteria:

1. Documentation of a previous diagnosis of polycythemia vera as defined by the WHO criteria
2. Bone marrow fibrosis grade 2–3 (on 0–3 scale) or grade 3–4 (on 0–4 scale)4,a

#### Additional criteria (two are required):

1. Anemiab or sustained loss of requirement of either phlebotomy (in the absence of cytoreductive therapy) or cytoreductive treatment for erythrocytosis
2. A leukoerythroblastic peripheral blood picture
3. Increasing splenomegaly defined as either an increase in palpable splenomegaly of  $\geq 5$  cm (distance of the tip of the spleen from the left costal margin) or the appearance of a newly palpable splenomegaly
4. Development of  $\geq 1$  of three constitutional symptoms: >10% weight loss in 6 months, night sweats, unexplained fever ( $>37.5^{\circ}\text{C}$ )

Abbreviations: IWG-MRT, International Working Group for Myelofibrosis Research and Treatment; LDH, lactate dehydrogenase; post-ET MF, post-essential thrombocythemia myelofibrosis; post-PV MF, postpolycythemia veramyelofibrosis.

aGrade 2–3 according to the European classification: diffuse, often coarse fiber network with no evidence of collagenization (negative trichrome stain) or diffuse, coarse fiber network with areas of collagenization (positive trichrome stain). Grade 3–4 according to the standard classification: diffuse and dense increase in reticulin with extensive intersections, occasionally with only focal bundles of collagen and/or focal osteosclerosis or diffuse and dense increase in reticulin with extensive intersections with coarse bundles of collagen, often associated with significant osteosclerosis.

bBelow the reference range for appropriate age, sex, gender and altitude considerations.

Reference: Barosi G, Mesa RA, Thiele J, et al. Proposed criteria for the diagnosis of post-polycythemia vera and post-essential thrombocythemia myelofibrosis: a consensus statement from the international working group for myelofibrosis research and treatment. Leukemia.2008; 22:437-438.

## APPENDIX B3: POST-ESSENTIAL THROMBOCYTHEMIA MYELOFIBROSIS DEFINITION

### 2008 IWG-MRT Diagnostic Criteria for post-essential thrombocythemia myelofibrosis (post-ET MF)

#### Required criteria:

1. Documentation of a previous diagnosis of essential thrombocythemia as defined by the WHO criteria
2. Bone marrow fibrosis grade 2–3 (on 0–3 scale) or grade 3–4 (on 0–4 scale)4,a

#### Additional criteria (two are required):

1. Anemiab and a  $\geq 2 \text{ mg ml}^{-1}$  decrease from baseline hemoglobin level
2. A leukoerythroblastic peripheral blood picture
3. Increasing splenomegaly defined as either an increase in palpable splenomegaly of  $\geq 5 \text{ cm}$  (distance of the tip of the spleen from the left costal margin) or the appearance of a newly palpable splenomegaly
4. Increased LDH (above reference level)
5. Development of  $\geq 1$  of three constitutional symptoms: >10% weight loss in 6 months, night sweats, unexplained fever ( $>37.5^\circ\text{C}$ )

Abbreviations: IWG-MRT, International Working Group for Myelofibrosis Research and Treatment; LDH, lactate dehydrogenase; post-ET MF, post-essential thrombocythemia myelofibrosis; post-PV MF, postpolycythemia vera myelofibrosis.

aGrade 2–3 according to the European classification: diffuse, often coarse fiber network with no evidence of collagenization (negative trichrome stain) or diffuse, coarse fiber network with areas of collagenization (positive trichrome stain). Grade 3–4 according to the standard classification: diffuse and dense increase in reticulin with extensive intersections, occasionally with only focal bundles of collagen and/or focal osteosclerosis or diffuse and dense increase in reticulin with extensive intersections with coarse bundles of collagen, often associated with significant osteosclerosis.

bBelow the reference range for appropriate age, sex, gender and altitude considerations.

Reference: Barosi G, Mesa RA, Thiele J, et al. Proposed criteria for the diagnosis of post-polycythemia vera and post-essential thrombocythemia myelofibrosis: a consensus statement from the international working group for myelofibrosis research and treatment. Leukemia.2008; 22:437-438.

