## 4 STUDY POPULATION

### 4.1 Inclusion Criteria

Patients meeting the following criteria will be eligible to participate in the study:

1. Primary myelofibrosis, post-PV MF, or post-ET MF (As defined in Appendix B) that requires therapy, including patients with intermediate-1, intermediate-2, or high-risk MF according to the International Prognostic Scoring System (IPSS) (Appendix C), regardless of their JAK2 mutation status. Patients must have symptomatic palpable splenomegaly (at least 5 cm below the left costal margin in the mid-clavicular line by physical examination). For the Phase 2 portion, MF patients must have received prior JAK2 inhibitor therapy, and been found to be intolerant, or refractory/relapsed from prior JAK2 inhibitor therapy, based on investigator assessment.
2.  $\geq 18$  years old.
3. Eastern Cooperative Oncology Group (ECOG) Performance Status of  $\leq 3$  (see Appendix D).
4. Estimated life expectancy of  $\geq 12$  weeks.
5. Male or non-pregnant, non-lactating female patients. Male and female patients who are fertile and their partners must agree to use one of the following methods of contraception from screening through 90 days following discontinuation of study drug.
  - Complete abstinence from sexual intercourse
  - Double-barrier method (condom with spermicide in conjunction with the use of an intrauterine device [IUD] or diaphragm)
  - Tubal ligation or vasectomy (surgical sterilization)
6. Negative serum or urine pregnancy test within 7 days prior to the first dose of study drug (if patient is a female of childbearing potential).
7. Serum creatinine of  $\leq 1.5 \times$  the upper limit of normal (ULN) OR estimated creatinine clearance (CrCl)  $\geq 40$  ml/min/1.73 m^2 calculated using the Cockcroft and Gault equation:

$$\text{CrCl (mL/min)} = [(140 - \text{age (years)}) \times \text{weight (kg)}] / (\text{serum creatinine (mg/dL)} \times 72)$$

For females, multiply result by 0.85

Aspartate aminotransferase (AST) and alanine aminotransferase (ALT)  $\leq 3 \times$  ULN and total bilirubin  $\leq 1.5 \times$  ULN. If the total bilirubin is elevated

between 1.5 x and 3 x ULN, patients with a direct bilirubin  $\leq$ 1.5 X ULN are eligible during the Phase 2 portion.

8. Adequate bone marrow reserve, as demonstrated by:
  - Absolute neutrophil count (ANC)  $>1000/\mu\text{L}$  and
  - Platelet count  $\geq 25,000/\mu\text{L}$  without the assistance of growth factors or platelet transfusions.

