3. Clinical improvement (CI)	
Requires one of the following in the absence of both disease progression (as outlined below) and CR/PR assignment (CI response is validated only if it lasts for no fewer than 8 weeks)
 
(1) A minimum 2 -g/L increase in hemoglobin level or becoming transfusion independent (applicable only for patients with baseline hemoglobin level of less than 100 g/L).‡
 
(2) Either a minimum 50% reduction in palpable splenomegaly of a spleen that is at least 10 cm at baseline or a spleen that is palpable at more than 5 cm at baseline becomes not palpable.§
 
(3) A minimum 100% increase in platelet count and an absolute platelet count of at least <math>50,000 \times 10^9/L</math> (applicable only for patients with baseline platelet count below <math>50 \times 10^9/L</math>).
 
(4) A minimum 100% increase in ANC and an ANC of at least <math>0.5 \times 10^9/L</math> (applicable only for patients with baseline absolute neutrophil count below <math>1 \times 10^9/L</math>).

4. Progressive disease (PD)	Requires one of the following: 
	(1) Progressive splenomegaly that is defined by the appearance of a previously absent splenomegaly that is palpable at greater than 5 cm below the left costal margin or a minimum 100% increase in palpable distance for baseline splenomegaly of 5-10 cm or a minimum 50% increase in palpable distance for baseline splenomegaly of greater than 10 cm.
	(2) Leukemic transformation confirmed by a bone marrow blast count of at least 20%.
	(3) An increase in peripheral blood blast percentage of at least 20% that lasts for at least 8 weeks.
5. Stable disease (SD)	None of the above.
6. Relapse	Loss of CR, PR, or CI. In other words, a patient with CR or PR is considered to have undergone relapse when he or she no longer fulfills the criteria for even CI. However, changes from either CR to PR or CR/PR to CI should be documented and reported.

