
* Because of subjectivity in peripheral blood smear interpretation, CR does not require absence of morphologic abnormalities of red cells, platelets, and neutrophils.
 
† In patients with CR, a complete cytogenetic response is defined as failure to detect a cytogenetic abnormality in cases with a pre-existing abnormality. A partial cytogenetic response is defined as 50% or greater reduction in abnormal metaphases. In both cases, at least 20 bone marrow- or peripheral blood-derived metaphases should be analyzed. A major molecular response is defined as the absence of a specific disease-associated mutation in peripheral blood granulocytes of previously positive cases. In the absence of a cytogenetic/molecular marker, monitoring for treatment-induced inhibition of endogenous myeloid colony formation is encouraged. Finally, baseline and posttreatment bone marrow slides are to be stained at the same time and interpreted at one sitting by a central review process.
 
‡ Transfusion dependency is defined by a history of at least 2 units of red blood cell transfusions in the last month for a hemoglobin level of less than 85 g/L that was not associated with clinically overt bleeding. Similarly, during protocol therapy, transfusions for a hemoglobin level of 85 g/L or more is discouraged unless it is clinically indicated.
 
§ In splenectomized patients, palpable hepatomegaly is substituted with the same measurements.
 
   It is acknowledged that worsening cytopenia might represent progressive disease, but its inclusion as a formal criterion was avoided because of the difficulty distinguishing disease-associated from drug-induced myelosuppression. However, a decrease in hemoglobin level of 20 g/L or more, a 100% increase in transfusion requirement, and new development of transfusion dependency, each lasting for more than 3 months after the discontinuation of protocol therapy, can be considered disease progression.
	

ANC = absolute neutrophil count; CR = complete remission; CI = clinical improvement; PD = progressive disease; PR = partial response; SD = stable disease.
	

Source: Tefferi A, Barosi G, Mesa R, et al. International Working Group (IWG) consensus criteria for treatment response in myelofibrosis with myeloid metaplasia, for the IWG for Myelofibrosis Research and Treatment (IWG-MRT). *Blood*. 2006;108:1497-1503.

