Anemia response	
Transfusion-independent patients: a <math>\geq 20</math> g/L increase in hemoglobin level  
 
Transfusion-dependent patients: becoming transfusion-independent{

Spleen response#	A baseline splenomegaly that is palpable at 5-10 cm, below the LCM, becomes not palpable   or
	A baseline splenomegaly that is palpable at $>10$ cm, below the LCM, decreases by $\geq 50\%**$
	A baseline splenomegaly that is palpable at $<5$ cm, below the LCM, is not eligible for spleen response
	A spleen response requires confirmation by MRI or computed tomography showing $\geq 35\%$ spleen volume reduction
Symptoms response	A $\geq 50\%$ reduction in the MPN-SAF TSS††

Progressive disease ‡‡	Appearance of a new splenomegaly that is palpable at least 5 cm below the LCM or
	A $\geq 100\%$ increase in palpable distance, below LCM, for baseline splenomegaly of 5-10 cm or
	A 50% increase in palpable distance, below LCM, for baseline splenomegaly of $>10$ cm or
	Leukemic transformation confirmed by a bone marrow blast count of $>20\%$ or A peripheral blood blast content of $\geq 20\%$ associated with an absolute blast count of $\geq 1 \times 10^9/L$ that lasts for at least 2 weeks
Stable disease	Belonging to none of the above listed response categories
Relapse	No longer meeting criteria for at least CI after achieving CR, PR, or CI, or
	Loss of anemia response persisting for at least 1 month or
	Loss of spleen response persisting for at least 1 month
Recommendations for assessing treatment-induced cytogenetic and molecular changes	
Cytogenetic remission	At least 10 metaphases must be analyzed for cytogenetic response evaluation and
	requires confirmation by repeat testing within 6 months window
	CR: eradication of a preexisting abnormality
	PR: $\geq 50\%$ reduction in abnormal metaphases (partial response applies only to patients with at least ten abnormal metaphases at baseline)
Molecular remission	Molecular response evaluation must be analyzed in peripheral blood granulocytes and
	requires confirmation by repeat testing within 6 months window
	CR: Eradication of a pre-existing abnormality
	PR: $\geq 50\%$ decrease in allele burden (partial response applies only to patients with at least 20% mutant allele burden at baseline)
Cytogenetic/molecular relapse	Re-emergence of a pre-existing cytogenetic or molecular abnormality that is confirmed by repeat testing

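### Hemoglobin-change thresholds in Appendix B3 (post-ET MF entry) and Appendix I (clinical improvement) are printed at one tenth of the 20 g/L used elsewhere in Appendices I and K and need reconciling

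*Combined protocol and SAP*

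**What the plan says.** Inclusion criterion 1 (Section 4.1) admits "Primary myelofibrosis, post-PV MF, or post-ET MF (As defined in Appendix B) that requires therapy", so the appendix definitions decide who enters. Appendix B3 requires a documented earlier diagnosis of essential thrombocythemia and marrow fibrosis of grade 2-3 (or 3-4 on the other scale). It then lists five further items under "Additional criteria (two are required"). The first item combines anemia, footnoted as "Below the reference range for appropriate age, sex, gender and altitude considerations", with a "decrease from baseline hemoglobin level" of at least 2 mg/ml.

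Appendix I, the Phase 1 response criteria, lists as its first route to clinical improvement: "A minimum 2 -g/L increase in hemoglobin level or becoming transfusion independent". It applies only to a baseline hemoglobin below 100 g/L, and the improvement must last at least 8 weeks. Section 12.4 counts clinical improvement in the objective response rate.

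Three other places use 20 g/L:
- the Appendix I footnote on progression, which refers to "a decrease in hemoglobin level of 20 g/L or more";
- the Appendix K anemia response for transfusion-independent patients, at least a 20 "g/L increase in hemoglobin level";
- the Appendix K definition of worsening anemia, a fall of at least 20 g/L from pretreatment baseline lasting 12 weeks.

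**The concern.** A tenfold gap between hemoglobin thresholds in one protocol suggests a unit problem, and both of the small values are in working definitions.

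In Appendix B3 the fall is an extra requirement on top of anemia. The parallel item for post-PV MF in Appendix B2 lists anemia without any stated fall, so the post-ET wording is evidently meant to ask for more. At 0.2 g/dL it asks for very little more.

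In Appendix I the small value affects a reported result. Preliminary efficacy is a secondary Phase 1 objective, and the response rate is given by dose level. Planned cohorts have 3 to 6 patients, so one patient classified differently moves a cohort's rate by 1/6 = 17 to 1/3 = 33 percentage points.

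**Working it through.** **Conversion.** 1 mg/ml = (1/1000 g)/(1/1000 L) = 1 g/L. So 2 mg/ml = 2 g/L = 0.2 g/dL, and 20/2 = 10.

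**Side by side.**

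| Place | Use | Change printed |
|---|---|---|
| Appendix B3, additional item 1 | post-ET MF entry | fall of 2 g/L |
| Appendix I, clinical improvement item 1 | Phase 1 response | rise of 2 g/L |
| Appendix I, progression footnote | worsening after therapy stops | fall of 20 g/L |
| Appendix K, anemia response | Phase 2 response | rise of 20 g/L |
| Appendix K, worsening of anemia | Phase 2, bars clinical improvement | fall of 20 g/L |

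The closest comparison is Appendix I item 1 with the Appendix K anemia response. Both concern a hemoglobin rise from a baseline below 100 g/L, and they differ tenfold. For Appendix B3 there is no second diagnostic value to compare with, so the other rows show the scale used but not what B3 should say.

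**Chance falls.** The documents give no hemoglobin measurement SD. Assume a single-measurement SD s of 2 to 7 g/L, two independent normal readings and no true change. Then P(apparent fall ≥ d) = 1 − Φ(d/(s√2)).

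| s (g/L) | d = 2 g/L | d = 20 g/L |
|---|---|---|
| 2 | 24.0% | below 0.001% |
| 3 | 31.9% | below 0.001% |
| 5 | 38.9% | 0.23% |
| 7 | 42.0% | 2.2% |

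By symmetry the same one-off probabilities apply to a rise. They overstate the chance of an Appendix I response, which must persist for 8 weeks.

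**Selection when hemoglobin has truly fallen.** Assume a normal true fall with mean m of 1 to 3 g/dL and SD 1.5 g/dL (again not in the documents). The share with a fall of at least t is 1 − Φ((t − m)/1.5).

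| m (g/dL) | any fall | ≥ 0.2 g/dL | ≥ 2 g/dL |
|---|---|---|---|
| 1 | 74.8% | 70.3% | 25.2% |
| 2 | 90.9% | 88.5% | 50.0% |
| 3 | 97.7% | 96.9% | 74.8% |

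Of patients with any fall, the printed limit keeps 70.3/74.8 = 94% to 96.9/97.7 = 99%. A limit ten times larger would keep 25.2/74.8 = 34% to 74.8/97.7 = 77%. The larger limit is shown only to give the size of the gap.

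**Effect on eligibility.** The anemia item decides entry only for a post-ET patient who has prior ET and the required fibrosis, and who needs this item to reach two of five. The other items are a leukoerythroblastic picture, increasing spleen, raised LDH and constitutional symptoms. Entry also states "Patients must have symptomatic palpable splenomegaly (at least 5 cm below the left costal margin" in the mid-clavicular line. That often overlaps with the spleen item but does not guarantee it, because Appendix B3 asks for a newly palpable spleen or an increase of at least 5 cm.

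**The case against.** The strongest reply is that nothing in the documents shows which value is wrong. Appendix B3 is presented as a published consensus definition, and the protocol may have copied it faithfully. The 20 g/L figures are response or worsening thresholds during or after therapy, and a diagnostic item may properly use a different one. This stands: a reader might infer that 20 g/L is the intended value for Appendix B3, but the documents do not establish that.

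A reader might also infer that any anemic patient completes the diagnosis, or that a quarter or more of post-ET patients would be wrongly admitted. Neither follows. On the same assumptions, 58 to 76% of patients with no true change would fail the 2 g/L limit. A patient whose earlier hemoglobin was in the reference range and is now below it has fallen by definition, so the noise model mainly concerns patients already anemic or near the limit at baseline. The documents do not say how many there are.

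The printed 2 in Appendix I has an irregular space before the hyphen and could be a character lost when the file was read, so that value should be checked in the original PDF. The unit in Appendix B3 is written out explicitly and does not look like such a fault.

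Finally, Section 12 plans no analysis by MF subtype and no formal efficacy test, so the entry item changes no planned comparison. That limits the weight of the Appendix B3 part. It does not answer the Appendix I part, because Section 12.4 reports the response rate. One qualification remains there: the synopsis paragraph on statistical analyses describes that rate with complete and partial responses only, whereas the synopsis efficacy paragraph and Section 12.4 include clinical improvement.

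**Conclusion.** The tenfold mismatch is real, and both small values are operative as printed: one in an entry definition, the other in a Phase 1 response definition. The conversion and the factor of ten are exact and need no assumption. That the fall adds little selection among patients already anemic is supported by the two illustrations, which rest on an assumed measurement SD of 2 to 7 g/L and an assumed distribution of true falls.

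The effect on eligibility is probably small. The effect on the Phase 1 response rate cannot be sized from the documents. It depends on how many patients with baseline hemoglobin below 100 g/L would qualify through a small sustained rise and by no other route. This is a minor point, worth correcting because it is cheap to settle.

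**What to change.** Check Appendix B3 item 1 and Appendix I clinical improvement item 1 against the published criteria each cites and against the 20 g/L passages in Appendices I and K. Then correct the units. If a source does print the smaller value, annotate it so that sites know the difference is deliberate. The platelet units deserve the same check: Appendix I asks for at least 50,000 × 10⁹/L in patients starting below 50 × 10⁹/L, and Appendix K gives a minimum of 25000 × 10⁹/L.

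Apply the reconciled hemoglobin thresholds when determining post-ET MF eligibility and Phase 1 clinical improvement. Hemoglobin is already collected at the scheduled visits, so no procedure, sample size or design feature changes.

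The cost is a short correction to two appendices. If the reconciled values are larger, a few post-ET patients may need a different additional criterion to qualify, and the Phase 1 response rate may be slightly lower.
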